2.6 STATISTICAL ANALYSIS

2.6.1 Statistical Analysis Plan

The analyses will describe the baseline demographic and clinical characteristics of the overall

population first by randomization unit (agency or combination of agencies), and then stratified by airway management strategy (standard management compared to initial SGA). A separate analysis for each step will be performed. For discrete variables, proportions will be generated and a chi-square test will be used to test for differences between the proportions. For continuous characteristics, means (medians) and standard deviations (interquartile ranges) will be calculated and t-tests (Wilcoxon) will be used to compare the means (distributions) among those with standard airway management vs. those managed by initial SGA. Variables that are imbalanced will be included as a covariate in multivariable models when assessing the association between strategy and outcomes.

We will calculate the difference in outcomes divided by the estimated “robust” standard error based on the Huber-White sandwich estimator in order to account for within-randomization unit correlation and variability, which might depart from the classical assumptions. To quantify the treatment effect, we will calculate the 95% confidence interval for the difference in event rates. We will perform the analysis on an intention-to-treat (primary analysis) and treatment-received (secondary analysis) bases.

Hypothesis #1: For the primary outcome, an indicator of death within 24 hours will be generated for each participant. A generalized linear mixed model (i.e. logistic regression model) will be used to assess the independent impact of initial SGAs on 24-hour survival, with a random effect of randomization unit a fixed effect for each step, and fixed effects of airway management (standard vs. initial SGA) and the potential confounding effects of baseline characteristics. The estimated intra-randomization unit correlation and time effect from this model will be reported to help design future randomized trials and to describe the potential confounding effects of calendar time. For time-to-event data, a mixed effects Cox-proportional hazards regression model will be used to assess the independent impact of airway management strategy on time to death, with randomization unit as a random effect and step, airway management strategy, and the potential confounding effects of baseline characteristics not balanced through random assignment as fixed effects.

Hypothesis #2: The same analytic approach that was carried out for hypothesis #1 will be implemented, but the outcome of interest will be survival to hospital discharge.

Hypothesis #3: The analytic approach for the secondary outcomes will vary based on the type of outcomes. For binary outcomes (e.g., 24-hour and in hospital mortality, ventilator associated pneumonia, and post-traumatic ARDS), the same analytic approach that was carried out for Hypothesis #1 will be implemented. For continuous outcomes (e.g., hypotension or hypoxia dose) a generalized linear mixed model (i.e., linear model) will be used to assess the independent effect of airway management strategy on outcome, with a random effect of randomization unit, a fixed effect for each step, and fixed effects of airway management strategy (standard airway versus initial SGA) and the potential confounding effects of baseline characteristics.

Subgroup Analysis: The general approach to assessing the homogeneity of a treatment effect across subgroups will be to include an interaction term between the use of airway management strategy (standard versus initial SGA) and the characteristics defining the subgroup in the regression model. A statistically significant interaction term would indicate that the null hypothesis of a homogenous effect can be rejected, indicating a differential effect from airway management strategy across the subgroups. For example, when examining the homogeneity of the effect of airway management strategy on the primary outcome among those with and without a TBI, the logistic model will be modified to include a main effect for TBI and the two-

way interaction between airway management strategy and TBI.

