2.6.2 Sample Size Determination

This stepped wedge randomized control trial will use 24-hour mortality as its primary outcome to power the trial. This sample size was calculated using the formula presented by Hemming and Taljaard and takes into account the design feature that airway management strategy will be switched from standard care to initial SGA sequentially by 17 prehospital agencies over 7 time periods (6 steps).¹⁷ The intra-randomization unit correlation coefficient (ICC) for the primary outcome was assumed to be 0.025 based on preliminary data from Pittsburgh's prehospital agencies. To detect a decrease from 16.7% to 9.7% (a difference of 7%), with 80% power at 5% significance level, a sample size of 1,904 will be required. To account for 5% dropout, we will need to enroll 118 participants from each of the 17 prehospital agencies over the seven enrollment periods (17 participants per agency per period). Therefore, the total required sample size is 2,006, however, to enroll equal numbers of patients in each enrollment period, we will enroll 2,009 patients.

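### Adjustment covariates are chosen by baseline balance tests that ignore clustering, so the adjusted model is not fixed in advance and strong predictors of 24-hour death are not guaranteed a place in it

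*Combined protocol and SAP*

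**What the plan says.** All of this is in section 2.6.1 (Statistical Analysis Plan).

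- Discrete baseline variables: "For discrete variables, proportions will be generated and a chi-square test will be used to test for differences between the proportions".
- Continuous ones: "t-tests (Wilcoxon) will be used to compare the means (distributions) among those with standard airway management vs. those managed by initial SGA".
- On time: "A separate analysis for each step will be performed". The word step is not defined there.
- The consequence of the tests: "Variables that are imbalanced will be included as a covariate in multivariable models when assessing the association between strategy and outcomes". This covers all strategy-outcome models.
- The primary logistic mixed model (Hypothesis #1) treats unit as random and step as fixed. Its other terms are listed as "fixed effects of airway management (standard vs. initial SGA) and the potential confounding effects of baseline characteristics", with none of those characteristics named.
- The Cox model for time to death, in the same paragraph, takes the "potential confounding effects of baseline characteristics not balanced through random assignment as fixed effects".

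No section lists adjustment covariates, sets a cut-off for imbalance, or keeps prognostic variables whatever their balance. Brain injury and air versus ground service appear in 2.6.3 only as subgroup factors.

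**The concern.** A balance test asks whether a variable differs between arms. It does not ask whether the variable predicts death, which is what determines the gain from adjusting for it. A weak predictor that happens to differ is taken in, and a strong one that happens to agree is left out.

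In this design the tests are also miscalibrated. Section 2.1.1 says agencies differ in crew makeup, transport mode, intubation drugs and adjuncts, so case mix will probably cluster by unit. An ordinary chi-square or t-test treats those patients as independent. Strategy is also tied to calendar time, because period 1 is all control and period 7 all SGA. A pooled test will therefore flag drift that the step effects in the outcome model already address.

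At stake is whether the primary model can be written down before arm-level data are seen. A conditional odds ratio also depends on which covariates are conditioned on, so changing the set changes what is estimated as well as its precision.

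**Working it through.** **1. The plan's own figure.** Section 2.6.2 gives 16.7% vs 9.7%, 80% power, 5% significance (taken as two-sided), ICC 0.025, 17 units and 7 periods.

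- Per arm, with mean rate 0.132: n = [1.96√(2×0.132×0.868) + 0.8416√(0.167×0.833 + 0.097×0.903)]² / 0.07² = 366.
- Stepped-wedge design effect with 6 steps and 16 patients per unit-period: (1 + 0.025×111)/(1 + 0.025×63) × 3×0.975/[2×(6 − 1/6)] = 1.466 × 0.2507 = 0.3676.
- Total: 2 × 366 × 0.3676 × 7 = 1,883, against 1,904 stated (1.1% apart).
- Dropout: 1,904/0.95 = 2,005, against 2,006.

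The figure is reproduced. No covariate enters it.

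**2. Inputs for the screen.** From the plan: 17 units, 7 periods, 17 patients per unit-period. Assumed, because the documents do not give them: units allocated 3,3,3,3,3,2 to the six steps, equal unit sizes, a two-sided 5% cut-off, covariate prevalence 30%, covariate ICC 0.025 to 0.10 (the lowest borrowed from the outcome), and drift of 0 or 5 percentage points over the trial.

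**3. Pooled test.** Units spend a = 6, 5, 4, 3, 2 or 1 periods on SGA.

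- SGA unit-periods: 3(6+5+4+3+2) + 2×1 = 62. Control: 119 − 62 = 57. Patients: 1,054 and 969.
- Each unit's mean enters the arm difference with weight w = a/62 − (7−a)/57, that is 0.0792, 0.0456, 0.0119, −0.0218, −0.0555 and −0.0891. Over the 17 units Σw² = 0.0520.
- The naive variance, in units of the covariate variance, is 1/1,054 + 1/969 = 0.001981.
- True over naive variance: R = (1−ICC) + ICC × 0.0520/0.001981 = (1−ICC) + 26.26×ICC.
- Chance of a flag without drift: 2Φ(−1.96/√R).
- With drift: mean enrolment period is 5.31 on SGA and 2.58 on control, a gap of 2.73/6 = 0.455 of the trial. A 5-point drift gives an expected difference of 0.05×0.455 = 0.0227. The naive SE is √(0.21×0.001981) = 0.0204, so the shift is 1.11 SE.

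| Covariate ICC | R | Flagged, no drift | Flagged, 5-point drift |
|---|---|---|---|
| 0 | 1.00 | 5% | 20% |
| 0.025 | 1.63 | 12.5% | 26% |
| 0.05 | 2.26 | 19% | 31% |
| 0.10 | 3.53 | 30% | 38% |

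Simulation agrees: about 13%, 20% and 30% without drift, and 25-38% with it.

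**4. Per-step tests.** If step means period, only periods 2 to 6 contain both arms. Drift is removed, but at ICC 0.025 R = 1 + 16×0.025 = 1.4, and 2Φ(−1.96/√1.4) = 9.8% per period. Simulation gives 9-11% each, and at least one flag in the five in about 38-41% of trials. If step means a row of Figure 2, each test is before against after: about 5% per row without drift and about 16% with a drift of 0.2 SD.

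**5. Omission.** The screen does not look at the outcome. At ICC 0.025 without drift the pooled test leaves a covariate out in 100 − 12.5 = 87.5% of trials, however strongly it predicts death.

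**6. Effect on the final analysis.** The rule was simulated with ten prognostic covariates, a random unit effect and fixed period effects (linear approximation; covariate strength assumed).

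- Type I error without drift, covariate ICC 0.025-0.10: 4.9-5.5% with selection, 5.7-6.1% when always adjusting.
- Power for a reduction of about 6.5 points at covariate ICC 0.05: 83.5% unadjusted, 84.5% with selection, 86.1% with all ten. Always adjusting gains 86.1 − 84.5 = 1.6 points over the rule and 86.1 − 83.5 = 2.6 over no adjustment. A further simulation put the gain at about 2-3 points.
- All ten covariates drifting the same way by 0.2 SD: type I error 5.7-7.8% with selection, 5.1-6.3% when always adjusting, and bias of about 1 percentage point.
- Range for the covariates' share of within-unit outcome variance (R², not in the documents), at N = 1,904: power 79.8% at 0, 81.6% at 0.05, 83.4% at 0.10 and 87.0% at 0.20. This compares full adjustment with none, so it overstates the loss from the rule, which admits some covariates.

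**The case against.** Four points can be made for the plan.

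- **Time.** A reader might infer that the balance tests ignore calendar time altogether. The documents do not support that: a separate analysis per step is planned and, if step means period, it conditions on time. What stands is that step is used both for time (the step effects, section 2.6.6) and for the rows of Figure 2, that the deciding comparison is not stated, and that no version accounts for clustering across units.
- **Scope.** A reader might infer that the primary model may contain only imbalanced variables. The restriction to characteristics not balanced by randomization is in the Cox sentence. The general rule says imbalanced variables go in, not that nothing else may. This stands, but a wider set is not named either, so the primary model is no better fixed.
- **Inference.** A reader might infer that the confidence interval and p-value are invalid because they ignore the selection. This is not shown. Selection uses baseline data and arm, not outcomes, and without drift simulated type I error stays near 5%.
- **Benign over-flagging.** An unneeded covariate costs little with 2,009 patients, unit and step are in the model regardless, and the sample size assumes no gain from covariates. All true. None of it secures the inclusion of the variables that matter most for prognosis.

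**Conclusion.** The concern holds as one of pre-specification and efficiency. The stated rule selects covariates by tests that ignore randomization unit, without a threshold or a stated deciding comparison, and no prognostic variable is guaranteed a place.

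Under the listed assumptions the pooled test flags a covariate unrelated to strategy at roughly two and a half to six times the nominal 5%, and more with drift. The consequence for the primary result is modest: an adjusted model not fixed in advance, about 2-3 points of power, and a possible small bias if case mix drifts strongly in one direction and the pooled test decides.

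The 5% cut-off, covariate ICCs, prevalence, drift and covariate strength are all assumptions. The wording and the absence of a covariate list are not. The change is worth making because it is cheap, not because the planned analysis has been shown to mislead.

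**What to change.** In section 2.6.1, replace the imbalance rule with a short list of prognostic covariates. They should be measured before the airway attempt, fixed before the first comparison by arm (so before the first interim analysis in 2.6.6), and used in the primary and secondary models together with unit and period. Candidates are age, sex, blunt versus penetrating mechanism, first GCS, first systolic pressure, first SpO2, air versus ground, and scene versus referral hospital.

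Confirm first that each is on the data form. Section 2.6.9 names vital signs and transport mode but not age, sex, GCS or mechanism, although its list is open-ended and other sections imply that most are recorded.

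Use the same list in the Cox model, and define step as period wherever time is meant. Make the baseline tables descriptive, with standardised differences and no significance tests. Report the model with unit and period only as a sensitivity analysis.

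The cost is SAP wording and imputation of some missing prehospital vital signs. The stated sample size does not change.

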2.1.1 Randomization

PACT will employ a stepped wedge design (Figure 2) in which all participating EMS agencies transition from the control arm, standard airway management strategy, to the intervention arm, initial SGA strategy, with some agencies applying the intervention before others¹⁵. Once an agency has stepped to the initial SGA arm, they will remain assigned to this arm for the remainder of the study. Blinding is not possible with this intervention. This trial design allows us to perform a pragmatic trial for an intervention strategy that has agency level variation as a result of differences in provider makeup (EMT/paramedic, dual paramedic, paramedic/nurse), transport mode (air/ground), the availability of rapid sequence intubation (RSI), the use of adjuncts (oropharyngeal and nasopharyngeal airways, tracheal introducers, video laryngoscopy), and training.

The trial will be conducted over approximately 48 months with 17 prehospital agencies crossing from standard care arm to intervention arm in one of seven periods. 287 subjects will be enrolled in each enrollment period, before stepping to the next enrollment period. This will continue until 1,722 subjects are enrolled, when all prehospital agencies will be exposed to the intervention arm.

Figure 2. Schematic illustration of the PACT stepped wedge randomized trial with six steps.

Approx. time	Year 1		Year 2		Year 3		Year 4	
Enrollment period →	287 subjects	574 subjects	861 subjects	1,148 subjects	1,435 subjects	1,722 subjects	2,009 subjects	
Step number ↓								
1								
2								
3								
4								
5								
6								

	Standard care (control arm)
	Initial SGA (intervention arm)

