2.6.6 Interim Analyses

Prior to initiation, and in concert with the DSMB, the final monitoring plan will be developed to serve as a guide to the DSMB's decision-making process concerning early stopping of the trial. In making the decision to recommend termination of the trial, the DSMB will be guided by information on safety outcomes by treatment group.

Two interim safety analyses will be conducted, one at the completion of the second step (third period) and one at the completion of the fourth step (fifth period, out of seven periods). The frequency of the composite safety outcome (mortality, failure to place an advanced airway on first attempt, failure to

ventilate) in the two groups will be summarized. The null hypothesis that there is no difference in the proportion of the rate of the composite safety outcome between the two groups will be tested using a generalized linear mixed model. Group sequential methods, such as a Lan and Demets approach with an O'Brien and Fleming spending function will be used to ensure that the overall type I error rate of 0.05 is maintained across the three tests (two interim and one final), with the majority of the type I error reserved for the final test. Based on the expected recruitment of 287 participants per period (2,009/7 periods), we expect a sample size of 861 for the first interim analysis (information fraction of 43%) and 1,435 for the second interim analysis (information fraction of 71%). For the first interim analysis the upper/lower boundaries will be ± 3.22 with a nominal alpha level of 0.001. The second interim analysis will have upper/lower boundaries of ± 2.42 with a nominal alpha level of 0.015. The final analysis will have upper/lower boundaries of ± 2.00 with a nominal alpha level of 0.045.

Further—and in relation to the interim safety analyses—safety data by group will be provided periodically to the DSMB. Safety data serious adverse events include frequency, a description of each event, and the date of each event.

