Appendix I – Study Sites

*All of the Oregon EMS agencies share training, standard protocols, and clinical competencies. Furthermore, they participate in mutual aid of trauma patients (more than one agency responding to and caring for a single patient). We will step all Oregon EMS agencies at the same time to ensure that patients enrolled in Oregon will have care that is consistent with a single randomization unit.

Site	EMS Agency	Participating Trauma Center(s)
Tulane University	New Orleans EMS	University Medical Center
University of Pittsburgh	City of Pittsburgh EMS	UPMC Presbyterian, UPMC Mercy, Allegheny General Hospital
University of Pittsburgh	STAT MedEvac	UPMC Presbyterian, UPMC Mercy, UPMC Altoona, UPMC Hamot, UPMC Susquehanna, Allegheny General Hospital
University of Pittsburgh	Emergycare	UPMC Hamot
University of Pittsburgh	Susquehanna Regional EMS	UPMC Susquehanna
Vanderbilt University	Nashville Fire	Vanderbilt University Medical Center
Emory University	Grady EMS	Grady Medical Center
University of Louisville	Louisville Metro EMS	University of Louisville Hospital
University of Louisville	St. Matthews EMS	University of Louisville Hospital
Washington University at St. Louis	Air Evac Lifeteam	Barnes-Jewish Hospital
Washington University at St. Louis	St. Louis Fire	Barnes-Jewish Hospital
East Carolina University	Vidant EastCare	Vidant Medical Center
East Carolina University	Pitt County EMS	Vidant Medical Center
East Carolina University	Wilson County EMS	Vidant Medical Center
East Carolina University	Lenoir County EMS	Vidant Medical Center
Oregon Health & Sciences University	American Medical Response*	Oregon Health & Sciences University Hospital
Oregon Health & Sciences University	Metro West Ambulance*	Oregon Health & Sciences University Hospital
Oregon Health & Sciences University	Hillsboro Fire*	Oregon Health & Sciences University Hospital
Oregon Health & Sciences University	Molalla Fire*	Oregon Health & Sciences University Hospital
Oregon Health & Sciences University	Canby Fire*	Oregon Health & Sciences University Hospital
Oregon Health & Sciences University	Tualatin Valley Fire & Rescue*	Oregon Health & Sciences University Hospital
Oregon Health & Sciences University	Clackamas Fire District 1*	Oregon Health & Sciences University Hospital
Oregon Health & Sciences University	Lake Oswego EMS*	Oregon Health & Sciences University Hospital
Cook County/Chicago	Chicago Fire Department	John H. Stroger Jr. Hospital of Cook County

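### The plan uses a Huber-White standard error with 17 randomisation units and no small-sample correction, leaves open whether that statistic decides the primary outcome, and states 80% power from normal quantiles (about 74% with t on 15 df).

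*Combined protocol and SAP*

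**What the plan says.** **The comparison.** The general part of section 2.6.1 forms a ratio of the outcome difference to a robust "standard error based on the Huber-White sandwich estimator in order to account for within-randomization unit correlation and variability". It then promises a 95% interval for the risk difference and makes intention-to-treat the primary basis. It names no reference distribution, degrees of freedom or small-sample correction.

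**The model.** Under Hypothesis #1, the same section assigns 24-hour survival to a logistic mixed model with a random unit effect, fixed step effects and a fixed strategy effect. It does not say whether that model uses model-based or sandwich standard errors.

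**The number of units.** Section 2.1.1 has "17 prehospital agencies crossing from standard care arm to intervention arm". Appendix I lists 24 agencies, but its note says "We will step all Oregon EMS agencies at the same time". The eight Oregon agencies therefore count once: 24 - 8 + 1 = 17.

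**Power.** Section 2.6.2 bases the calculation on switching "sequentially by 17 prehospital agencies over 7 time periods (6 steps"), with an ICC that "was assumed to be 0.025 based on preliminary data". The target is: "To detect a decrease from 16.7% to 9.7% (a difference of 7%), with 80% power at 5% significance level". The result is 1,904 analysable patients, with equal enrolment per agency.

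**The concern.** The plain sandwich estimator is biased downward when clusters are few, and a normal reference then adds to the problem by ignoring the uncertainty in the standard error itself. Seventeen units is few enough for both effects to matter. Unequal unit sizes would make it worse. Appendix I mixes an air service feeding six hospitals, a merged eight-agency unit and single-county services, so inequality is plausible although no volumes are given.

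If this statistic settles the primary comparison, the trial's false-positive rate is above the stated 5%. If it only supplies the risk-difference interval, that interval still covers too rarely. The second possibility is realistic: the interval is described directly after the sandwich sentence, and a logistic mixed model does not directly yield a risk difference.

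The sample-size calculation has a related but separate weakness. It also uses normal quantiles, so the stated power is optimistic for any test that allows for 17 units.

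**Working it through.** **1. Inputs.** From 2.6.2: I = 17 units, T = 7 periods, ICC 0.025, rates 16.7% and 9.7%, alpha 0.05, and 1,904 = 17 x 7 x 16, so m = 16 per unit-period. Assumptions: a two-sided test (2.6.2 does not say) and units split 3,3,3,3,3,2 over the six steps (the split is not stated).

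**2. Reproducing the stated power.** Hussey-Hughes stepped-wedge variance with period effects:

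Var = I s2 (s2 + T t2) / [(IU - W) s2 + (U^2 + ITU - TW - IV) t2]

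- Average binomial variance: (0.167 x 0.833 + 0.097 x 0.903)/2 = 0.11335.
- t2 = 0.025 x 0.11335 = 0.002834; s2 = 0.975 x 0.11335/16 = 0.006907.
- For this layout U = 62, W = 784, V = 272, so IU - W = 1,054 - 784 = 270, and the second bracket is 3,844 + 7,378 - 5,488 - 4,624 = 1,110.
- Var = 17 x 0.006907 x 0.026744 / (1.8650 + 3.1455) = 0.0006268, so SE = 0.02504.
- 0.07/0.02504 = 2.796, and power with a normal reference is Phi(2.796 - 1.960) = 79.8%.

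The stated 80% is reproduced.

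**3. The same SE with a t reference.** Power is the probability that a non-central t with non-centrality 2.796 exceeds the t critical value.

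| Reference | Critical value | Power at 1,904 |
|---|---|---|
| Normal | 1.960 | 79.8% |
| t, 16 df | 2.120 | 74.7% |
| t, 15 df (units minus 2) | 2.131 | 74.3% |
| t, 9 df | 2.262 | 70.2% |

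If all 2,009 are analysed, m = 2,009/119 = 16.88, SE = 0.02445 and the ratio is 2.863. Power is then 76.3% with t on 15 df.

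Simulated power for corrected sandwich tests, with equal units and an exchangeable working correlation, is:
- Kauermann-Carroll with t15: 75-76%
- Fay-Graubard with t15: 76-77%
- Fay-Graubard with t9: 72-73%
- Mancl-DeRouen with z: 76-77%
- Mancl-DeRouen with t15: 71%

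The overall range is about 70-77%. It presupposes that weighting: with an independence working correlation, a smaller run (1,000 trials) gave 63% for Kauermann-Carroll and 57% for Mancl-DeRouen, both with t15.

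**4. Type I error.** Null trials were simulated on the 17-unit, 7-period layout with base risk 16.7%, ICC 0.025 and 16 per unit-period on average. The uncorrected sandwich was judged against the normal distribution.

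| Unit sizes | Working correlation | Rejection rate |
|---|---|---|
| Equal, logistic, period-adjusted | exchangeable | 8.7-9.8% |
| Equal, logistic, period-adjusted | independence | 9.0-9.6% |
| Equal, linear, period-adjusted | exchangeable | 9.5% |
| Equal, linear, period-adjusted | independence | 9.1-10.2% |
| CV 0.5 (assumed), linear | independence / exchangeable | 10.4% / 8.5% |
| CV 0.8 (assumed), linear | independence / exchangeable | 12.3% / 8.5% |

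The equal-size rows use 4,000 trials (Monte Carlo SE about 0.5 points) and the CV rows 2,000. Two further equal-size sets of 2,000 trials gave 7.8-9.7% and 8.5-8.9%, and omitting period effects gave about 8%. At the null, 8-10% rejection means that a nominal 95% interval covers about 90-92% of the time.

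With the Mancl-DeRouen correction and t15, rejection in the linear runs (equal sizes, CV 0.5 and CV 0.8) was 3.3-4.7%. The model-based z-test from the exchangeable model, used as a proxy for the mixed model, rejected 5.6-6.0%.

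**The case against.** The strongest reply is that the sandwich ratio is not the primary test. Under Hypothesis #1 the plan names a logistic mixed model for the primary outcome, and that model's z-test is close to nominal. This stands as far as it goes. A reader might infer that the primary false-positive rate is simply double the stated 5%, but the documents do not support that. It follows only if the sandwich statistic decides, and the plan is silent on that.

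A reader might also take "The final analysis will have upper/lower boundaries of ± 2.00 with a nominal alpha level of 0.045" in 2.6.6 as proof that the sandwich statistic will be judged against normal limits. Those boundaries are set out for a composite safety outcome tested with a mixed model. A normal reference for the sandwich ratio is the likely default, but it is inferred from silence.

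Third, a general figure of 10-13% for type I error would go too far. Section 2.6.2 plans equal enrolment, which gives about 8-10%; anything clearly higher needs an assumed spread of unit sizes.

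Fourth, the fall in power should not be blamed on the sandwich. The 79.8% comes from a model-based variance, and the loss comes from replacing normal by t quantiles.

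These points narrow the finding but do not remove it. No correction appears for either method, and the choice between a test with roughly 6% error and one with 8-10% is left open.

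**Conclusion.** The concern holds in a conditional form. As written, the plan allows an uncorrected sandwich test or interval with 17 units. With a normal reference, that has about 8-10% type I error at equal unit sizes, and roughly 9-13% at an assumed size CV of 0.5-0.8. The mixed model's own z-test, at about 5-6%, is a minor problem by comparison. The fault is therefore an anti-conservative standard error combined with an undeclared primary test; it is not an established doubling of the trial's error rate.

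Independently of which test is chosen, "with 80% power at 5% significance level, a sample size of 1,904 will be required" is a normal-approximation statement. With t on 15 df, power is about 74% at 1,904 and about 76% if all 2,009 are analysed, within a range of about 70-77% across common corrections. These figures assume a two-sided test, equal unit sizes, ICC 0.025, the assumed split of units over steps, no gain from the planned covariate adjustment and, for the simulated sandwich tests, exchangeable weighting.

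**What to change.** 1. In 2.6.1, name the step-adjusted mixed model as the primary test of 24-hour mortality, and give it a small-sample reference, for example t on 15 df (units minus 2).
2. Where a sandwich standard error is kept for the risk-difference interval, use the Kauermann-Carroll or Mancl-DeRouen version with t on 15 df, and state the working correlation. If agency volumes turn out very unequal, Mancl-DeRouen is the safer choice: at an assumed CV of 1.0, rejection was 3.6-5.2% with it and 5.2-8.6% with Kauermann-Carroll.
3. In 2.6.2, restate the power for the chosen test: about 74% for t on 15 df at 1,904 with equal units. Put beside it a figure based on the agencies' expected volumes.

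The cost is SAP wording, settled before the outcome analysis. The critical value rises from 1.960 to 2.131, and 2.131/1.960 = 1.087, so intervals are about 9% wider from the t reference alone and somewhat more where the sandwich is also bias-corrected. The stated power becomes less favourable. No extra patients are needed.

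### The risk difference and its 95% CI are specified without a stated period adjustment or a link to the step-adjusted primary model, so as written they can absorb calendar time

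*Combined protocol and SAP*

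**What the plan says.** Section 2.6.1 describes the effect on 24-hour mortality in two places.

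- **General paragraphs.** The test statistic is introduced as "We will calculate the difference in outcomes divided by the estimated “robust” standard error based on the Huber-White sandwich estimator", and the reason given is correlation and variability within randomization units. Next comes "To quantify the treatment effect, we will calculate the 95% confidence interval for the difference in event rates". Neither sentence mentions step, period or a model. On covariates, the paragraph before says "Variables that are imbalanced will be included as a covariate in multivariable models when assessing the association between strategy and outcomes"; period is not named there.
- **Hypothesis #1 paragraph.** The primary outcome gets a logistic mixed model "with a random effect of randomization unit a fixed effect for each step, and fixed effects of airway management (standard vs. initial SGA"), plus baseline characteristics. The plan adds that the "time effect from this model will be reported to help design future randomized trials and to describe the potential confounding effects of calendar time". Hypotheses #2 and #3 reuse this approach for other binary outcomes, and step is also a fixed effect in the Cox and linear models.

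On the design, section 2.1.1 says "Once an agency has stepped to the initial SGA arm, they will remain assigned to this arm for the remainder of the study". Section 2.6.2 powers the trial on a difference in event rates, 16.7% to 9.7%.

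**The concern.** In a one-way stepped wedge, control patients are enrolled earlier on average than SGA patients. Any change over about 48 months in case mix, hospital care or background mortality therefore enters an unadjusted comparison of arms. A sandwich standard error repairs the variance; it does nothing about this bias.

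The step-adjusted model deals with time, but its direct output is an odds ratio, and the plan gives no route from it to a difference in event rates. The two descriptions also handle clustering differently (random effect in one, sandwich standard error in the other), which makes it hard to read them as one analysis. The risk difference is the only effect measure in section 2.6.1 with a named confidence interval, and it is on the scale of the design effect, so it is likely to be a headline result. An analyst could follow the text faithfully and report a time-confounded risk difference beside a time-adjusted odds ratio, with no rule for which governs if they disagree.

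**Working it through.** **1. Inputs.** From sections 2.1.1 and 2.6.2: 17 agencies, 7 periods, 6 steps, ICC 0.025, 16.7% versus 9.7%, 80% power, 5% significance, N = 1,904 before dropout, 287 subjects per period. Assumed: two-sided test; equal agency sizes; agencies split 3, 3, 3, 3, 3, 2 over the six steps; first period all control and last all SGA (implied by six steps over seven periods).

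**2. The plan's sample size reproduces.** Two proportions, individually randomized: 366 per arm, 732 in total. The stepped-wedge design effect with k = 6 steps, one baseline period and m patients per agency-period is

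[1 + ρ(km + m − 1)] / [1 + ρ(km/2 + m − 1)] × 3(1 − ρ) / [2(k − 1/k)].

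- m = 16: (3.775/2.575) × (2.925/11.667) = 0.3676; 0.3676 × 732 × 7 = 1,883.
- m = 17: 0.3702 × 732 × 7 = 1,897.

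In whole patients, 17 × 16 × 7 = 1,904. As a cross-check, the Hussey–Hughes variance, which includes fixed period effects, gives a standard error of 2.50 points at m = 16 (average of the two arms' binomial variances). Power is Φ(7/2.50 − 1.96) = 79.8%. The stated size therefore already allows for period adjustment. With the control-arm variance throughout, power would be 71.4%.

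**3. Share of a linear trend absorbed by an unadjusted difference.** This is the gap between the arms' mean enrollment periods, divided by the 6 intervals from period 1 to period 7.

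| Layout | Mean period, SGA | Mean period, control | Share |
|---|---|---|---|
| Six equal sequences | 112/21 = 5.33 | 56/21 = 2.67 | 2.67/6 = 44% |
| 17 agencies, 3,3,3,3,3,2 | 329/62 = 5.31 | 147/57 = 2.58 | 2.73/6 = 45% |

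**4. Size.** The documents give no secular trend, so the first column is an assumption. The simulation had no true SGA effect, 3,000 trials per row, m = 17, a linear probability model, a cluster-robust standard error and a critical value of 1.96. The adjusted analysis had fixed period and unit terms.

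| Assumed total fall (points) | Simulated mean of unadjusted difference (points) | Rejection, unadjusted | Rejection, period- and unit-adjusted |
|---|---|---|---|
| 0 | 0.06 | 6.8% | 7.2% |
| 1 | −0.45 | 7.5% | 7.4% |
| 2 | −0.92 | 9.0% | 7.5% |
| 3 | −1.34 | 12.5% | 7.1% |
| 5 | −2.20 | 22.7% | 7.9% |

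A 3-point rise gives +1.35 points and 12.5%, a spurious harm. The adjusted estimate stays within 0.05 points of zero in every row. Its 7–8% rejection comes from an uncorrected sandwich standard error with 17 units, not from time.

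**5. What adjustment costs in precision.** With a true 7-point effect and no trend, simulated power was 94.9% unadjusted and 75.8% adjusted. The adjusted analysis used fixed unit effects, which discard between-unit information that a random effect keeps; step 2 gives the mixed-model figure. The unadjusted figure is not a fair benchmark, because it relies on there being no trend.

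**The case against.** The strongest reply is that the general paragraphs are preamble and the Hypothesis #1 paragraph is the operative analysis. That paragraph names the primary outcome, includes "with a random effect of randomization unit a fixed effect for each step" and recognises confounding by calendar time. The subgroup section also treats the logistic model as the one for the primary outcome. This stands: a reader who inferred that the plan ignores time would be wrong.

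A reader might also infer that the plan labels the unadjusted contrast as its primary analysis, from "We will perform the analysis on an intention-to-treat (primary analysis"). The documents do not support that. The sentence goes on to call the treatment-received analysis secondary, so the label distinguishes analysis populations, not statistical methods.

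Nor does the text say that the difference is unadjusted. It is silent, and a difference with a sandwich standard error can come from a regression. That too stands, and it is why the point is conditional. Finally, the bias needs a trend, the documents give none, and part of the excess rejection (6.8% at no trend) has nothing to do with time.

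What remains is that a logistic mixed model does not itself give a difference in event rates. The plan asks for that difference with a CI and does not say how to get it with period adjusted.

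**Conclusion.** The concern holds in a limited form. The plan has a sound step-adjusted model for the primary outcome. It also promises a risk difference and 95% CI, on the scale of the design effect, with no stated period adjustment and no link to that model. Computed as the text reads, the difference would carry 44–45% of any linear change in 24-hour mortality across the trial: about 0.45 points for an assumed 1-point change and about 2.2 for 5 points, with simulated false-positive rates of 7.5% and 22.7% against a no-trend baseline of 6.8%.

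The share rests on roughly equal agency sizes, near-equal sequences and a linear trend. The biases and error rates rest also on drifts that are assumed, and they are not a forecast that the trial's error rate will be inflated. If the sponsor already intends a model-based difference, the defect is one of wording only.

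**What to change.** In section 2.6.1:

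- State that the primary analysis of 24-hour mortality is the Hypothesis #1 mixed model on intention-to-treat patients.
- Define step in that model as the seven enrollment periods. Figure 2 uses step number for six rows and enrollment period for seven columns, so the present term is ambiguous.
- Obtain the risk difference and its 95% CI from that model by marginal standardisation, or from a step-adjusted linear mixed model, and report the odds ratio beside it.
- Show crude event rates by arm and period as descriptive only, without a test.
- If a sandwich standard error is kept anywhere, state a small-sample correction for 17 units.

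The cost is SAP wording and a little programming. The interval will be wider than an unadjusted one. No extra patients are needed, because 1,904 already gives about 80% power with period effects under the assumptions shown above.
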